3.7.1 General Inpatient Procedures

Subjects will remain either in a seated or semi recumbent position for the first 4 hours following IMP administration except during brief periods where protocol related procedures need to be performed.

3.7.2 Dietary Requirements

See Section 3.2 Trial Treatments.

3.7.3 Schedule of Assessments

3.7.3.1 Screening (for All Cohorts)

Prior to initiation of any protocol-related procedures, the procedures and characteristics of the trial will be explained to the subject and written informed consent will be obtained from the subject (and the subject's legal representative if the subject is a minor or is hospitalized for reasons of medical protection). The following subject information will be recorded on source documents and the electronic case report form (eCRF).

- Date of informed consent
- Subject identifier
- Previous subject identifier, if the subject was rescreened
- Date of informed consent for CYP2D6 genetic testing*
- Date of informed consent for DNA storage (optional)*
- * Informed consent will be obtained before blood sampling for CYP2D6 genetic testing and blood sampling for DNA storage (optional).

In cases where subjects withdrawn from the trial at the discretion of the sponsor subsequently take part in the trial again and resume participation in the same cohort, the procedures and characteristics of the trial will be explained to them and written informed consent will be obtained from them (and their legal representatives if they are minors or are hospitalized for reasons of medical protection) prior to initiation of any protocol-related procedures. The following subject information will be recorded on the source documents and the eCRF.

- Date on which informed consent was obtained again
- Subject identifier
- Date of informed consent for CYP2D6 genetic testing^{**}
- Date of informed consent for DNA storage (optional)**
- ** Informed consent will be obtained before blood sampling for CYP2D6 genetic testing and blood sampling for DNA storage (optional). However, if blood samples had already been collected before the subject was withdrawn from the trial, it will not be necessary to obtain consent again.

After informed consent is obtained, the following observations, tests, and assessments will be performed as screening procedures within 28 days before IMP administration in Period 1 (Days -28 to -1), and the subject's eligibility to participate in the trial will be assessed.

[Items]

- Inclusion/exclusion criteria
- Demographics (date of birth, sex, country [Japan], race, ethnicity, complications, medical history)
- Height, weight, and body mass index (BMI): Height will be measured in increments of 0.1 cm. For a height measured to the second or further decimal place, the number will be rounded off to the first decimal place. BMI will be determined based on height and weight measurements at screening, using the following formula: $BMI = weight (kg) / height (m)^2$.
- Urine drug screening
- Urine pregnancy test (women of childbearing potential only)
- Clinical laboratory tests (blood and urine samplings)
- Physical examination
- Vital signs (blood pressure, pulse rate, and body temperature): Blood pressure and pulse rate will be measured in the supine position (performed first), sitting position, and standing position after each position is maintained for at least 3 minutes (blood pressure and pulse rate measurements in the supine and standing positions will take place only at screening).
- 12-Lead ECG (performed prior to blood sampling for clinical laboratory tests)
- C-SSRS (the "Baseline/Screening Version" will be used)
- AEs
- Concomitant medications and therapies

In cases where subjects withdrawn from the trial at the discretion of the sponsor subsequently take part in the trial again and resume participation in the same cohort, the following observations, tests, and assessments will be performed as screening procedures, after informed consent is obtained, within 28 days (Days -28 to -1) before IMP administration in the treatment period (Period 2 or 3) in which they are to resume participation in the trial, and their eligibility to participate in the trial will be assessed.

[Items]

- Inclusion/exclusion criteria
- Height,* weight, and BMI*: Height will be measured in increments of 0.1 cm. For a height measured to the second or further decimal place, the number will be rounded off to the first decimal place. BMI will be determined based on height and weight measurements at screening, using the following formula: BMI = weight (kg) / height (m)².
- * The height measurement obtained at screening when the subject first participated in the trial may be used. In that case, the height measurement obtained at screening when the subject first participated in the trial should be used in calculation of BMI.
- Urine drug screening

Confidential - Proprietary Information

- Urine pregnancy test (women of childbearing potential only)
- Clinical laboratory tests (blood and urine sampling)
- Physical examination
- Vital signs (blood pressure, pulse rate, and body temperature): Blood pressure and pulse rate will be measured in the supine position (performed first), sitting position, and standing position after each position is maintained for at least 3 minutes (blood pressure and pulse rate measurements in the supine and standing positions will take place only at screening).
- 12-Lead ECG (performed prior to blood sampling for clinical laboratory tests)
- C-SSRS (the "Since Last Visit" will be used)
- AEs
- Concomitant medications and therapies

3.7.3.2 Administration of Brexpiprazole Conventional Tablet (Period 1) (for All Cohorts)

3.7.3.2.1 Day 1 of Period 1

3.7.3.2.1.1 Enrollment of Subjects

On Day 1 of Period 1, one brexpiprazole conventional tablet will be administered to eligible subjects.

3.7.3.2.1.2 Within 1 Day Predose

The following will be performed.

- Pregnancy test
- Blood sampling for CYP2D6 genetic testing (including blood sampling for DNA storage [optional])
- Blood sampling for plasma drug concentration measurement (within 2 hours predose)
- Physical examination (within 2 hours predose)
- Vital signs (blood pressure, pulse rate, and body temperature) (within 2 hours predose)
- Weight
- 12-Lead ECG
- DIEPSS
- C-SSRS (The "Since Last Visit" will be used)
- CGI-S
- AEs
- Concomitant medications and therapies

12-Lead ECG may be omitted if IMP administration takes place within 14 days after the same test was performed during screening.

3.7.3.2.1.3 Postdose

The investigator or subinvestigator will perform the observations, tests, and assessments indicated in Table 3.7-1 and Table 3.7-2 and record their dates and results.

3.7.3.3 QW Formulation Single Administration Periods (Periods 2 and 3 of Cohort 1 and Cohort 1' [as Necessary])

The investigator or subinvestigator will enroll subjects who he/she thinks can safely receive IMP administration in Periods 2 and 3, perform the observations, tests, and assessments indicated in Table 3.7-1, and record their dates and results. Subjects withdrawn from the trial at the discretion of the sponsor will only be enrolled again to resume participation in the trial from Period 2 or 3 if they are confirmed to be eligible.

3.7.3.4 QW Formulation Repeated Administration Period (Period 2 of Cohort 2)

The investigator or subinvestigator will enroll subjects who he/she thinks can safely receive IMP administration in Period 2, perform the observations, tests, and assessments indicated in Table 3.7-2, and record their dates and results.

3.7.3.5 Follow-up After IMP Administration (for All Cohorts)

The following observations, tests, and assessments will be performed between Day 28 and Day 30 of Period 3 of Cohort 1 and Cohort 1' (as necessary) (single administration period) and between Day 56 and Day 60 of Period 2 of Cohort 2 (repeated administration period).

[Items]

- Physical examination
- DIEPSS
- AEs

3.7.4 Prior and Concomitant Medications

The investigator or subinvestigator will record on the source documents and eCRF all medications (name of drug, purpose of use, dose, frequency, route of administration, start and end dates of treatment) and therapies (name of therapy, purpose of use, start and end dates of treatment) taken by the subject from 30 days prior to signing of informed consent through the end of assessment on Day 14 of Period 3 or the end of early termination (ET) assessment in Cohort 1 and Cohort 1' (as necessary) (single administration period) and Confidential - Proprietary Information 65 Version 4.0, 18 Jun 2020

from 30 days prior to signing of informed consent through the end of assessment on Day 42 of Period 2 or the ET assessment in Cohort 2. The investigator or subinvestigator will record all medications (name of drug, purpose of use, dose, frequency, route of administration, start and end dates of treatment) and therapies (name of therapy, purpose of use, start and end dates of treatment) taken by the subject for treatment of an AE or which caused an AE until the end of the trial (defined as the last date of contact or date of final contact attempt) on the source documents and eCRF. For subjects who were withdrawn from the trial at the discretion of the sponsor and resume participation in the trial from Period 2 or 3, medications and therapies will be recorded in the same manner after participation in the trial at the discretion of the sponsor and terminated up to 30 days before the date on which the subject provided his/her signature for re-consent will be recorded as far as possible.

3.7.5 Safety Assessments

3.7.5.1 Adverse Events

Refer to Section 5 Reporting of Adverse Events for the methods and timing for assessing, recording, and analyzing AEs.

3.7.5.2 Clinical Laboratory Assessments

Data on laboratory test items shown in Table 3.7.5.2-1 will be collected at scheduled time points using measuring kits supplied by the central laboratory. The investigator or subinvestigator will review, sign, and date the laboratory assessment report submitted by the central laboratory and record the dates on which blood and urine samples are taken on the source documents and eCRF.

A pregnancy test (human chorionic gonadotropin [hCG] in urine) will be conducted in women of child-bearing potential (WOCBP) prior to trial intervention; results must be available prior to the administration of the IMP.

Table 3.7.5.2-1Clinical Laboratory Assessments			
Hematology	Serum Chemistry		
Hemoglobin	Alkaline phosphatase (ALP)		
Hematocrit	Alanine aminotransferase (ALT)		
Red blood cell (RBC) count	Aspartate aminotransferase (AST)		
White blood cell (WBC) count with differential	Albumin		
(neutrophils, lymphocytes, monocytes, eosinophils,	Bilirubin, total		
basophils)	Blood urea nitrogen (BUN)		
Platelet count	Uric acid		
	Cholesterol, total		
Urinalysis	Creatinine		
Occult blood	Gamma glutamyl transpeptidase (γ-GTP)		
Glucose	Glucose		
Microscopic analysis of RBC/WBC count (per high	Lactic dehydrogenase (LDH)		
powered field)	Serum electrolytes (Na, K, Cl, Ca, Mg, P,		
pH	HCO3)		
Protein	Protein total		
Ketones	Triglycerides		
Specific gravity	Creatine phosphokinase (CPK)		
	Prolactin		
	Glycosylated hemoglobin (HbA1c)		
	Insulin		
	Thyroid function test ^a		
	Thyroid-stimulating hormone (TSH), free		
	thyroxine (FT4)		

a	c 1	. 1	4 . *	• .	
‴Will he	e nertormed	at only	7. Etime	noint.	screening
W III 00	periorinea	ut only	i unno	pome.	sereening.

3.7.5.3 Urine Drug Screening

Data on the following items will be collected at scheduled time points using measuring kits supplied by the central laboratory. The investigator or subinvestigator will record the dates on which urine samples are taken on the eCRF.

- Amphetamines
- Barbiturates
- Benzodiazepines
- Cannabinoids
- Cocaine
- Marijuana
- Opiates
- Phencyclidine

3.7.5.4 Physical Examination and Vital Sign Assessments

A physical examination will be performed at scheduled time points. The physical examination includes the head, ears, eyes, nose, throat, chest, abdomen, urogenital system, limbs, nerves, skin, and mucosa.

At screening, all physical findings observed after informed consent will be recorded, together with the date of examination, on the source documents and eCRF. Thereafter, whether a physical examination is performed or not and, if performed, the date of examination will be recorded on the source documents and eCRF. For subjects who were withdrawn from the trial at the discretion of the sponsor and subsequently take part in the trial again, whether a physical examination is performed, the date of examination will be recorded on the source documents and subsequent time points and, if performed, the date of examination will be recorded on the source documents and subsequent time points and, if performed, the date of examination will be recorded on the source documents and eCRF.

It is preferable to have the same physician perform all physical examinations for any individual subject throughout the course of the trial wherever possible. Any new, clinically relevant, postscreening physical findings obtained from the start of the trial to the physical examination before IMP administration on Day 1 of Period 2 and any new, clinically relevant physical findings obtained after the start of IMP administration in Period 2 in comparison with those obtained before IMP administration on Day 1 of Period 2 will be recorded as AEs on the source documents and eCRF. For subjects who were withdrawn from the trial at the discretion of the sponsor and resume participation in the trial from Period 2, any new, clinically relevant physical findings obtained during the screening period in comparison with those obtained at the first screening before withdrawal and any new, clinically relevant physical findings obtained during Periods 2 and 3 in comparison with those obtained before IMP administration in Period 2 will be recorded as AEs on the source documents and eCRF. For subjects who were withdrawn from the trial at the discretion of the sponsor and resume participation in the trial from Period 3, any new, clinically relevant physical findings obtained during the screening period and Period 3 in comparison with those obtained before IMP administration in Period 2 before withdrawal will be recorded as AEs on the source documents and eCRF.

Vital signs will be measured at scheduled time points. Body temperature (axillary) will be measured in increments of 0.1°C and the date and result of measurement will be recorded on the source documents and eCRF. Blood pressure (systolic and diastolic) and pulse rate will be measured in a sitting position following at least 3 minutes' rest and the date and result of measurement will be recorded on the source documents and eCRF. At screening only, blood pressure and pulse rate will also be measured in the supine and standing positions.

Confidential - Proprietary Information

3.7.5.5 Weight

Weight will be measured at scheduled time points. Weight should be measured in 0.1 kg increments using the same scale and the standard measurement method (the subject should wear his/her usual clothes but without shoes) throughout the course of the trial. The date and result of measurement will be recorded on the source documents and eCRF.

3.7.5.6 Electrocardiogram Assessments

Electrocardiography will be performed at scheduled time points using a 12-lead electrocardiograph supplied by the central ECG laboratory.

An ECG will be taken after the subject has remained at rest for at least 5 minutes in a supine position. The heart rate, RR interval, PR interval, QRS interval, QT interval, and corrected QT interval (QTcF) will be measured. The central ECG laboratory will analyze the measurements and submit an ECG analysis report to the sponsor and the investigator or subinvestigator.

The investigator or subinvestigator will review, sign, and date each ECG reading by referring to the ECG analysis report and record the date of ECG, whether the ECG is normal/abnormal, and findings on the source documents and eCRF. The ECG should be performed prior to any blood sampling (if applicable) at scheduled time points.

3.7.5.7 Columbia-Suicide Severity Rating Scale

Columbia-Suicide Severity Rating Scale will be performed at scheduled time points. The C-SSRS assesses the occurrence, severity, and frequency of suicidal ideation/behavior during the assessment period. This assessment consists of the "Baseline/Screening Version," which assesses the history of suicide-related events and suicidal ideation in the lifetime and within the last 24 months, and the "Since Last Visit Version," which focuses on suicidality since the last assessment in the trial. The "Baseline/Screening Version" will be used at screening and the "Since Last Visit" will be used at subsequent time points for C-SSRS assessment. The date and result of assessment will be recorded on the source documents and eCRF.

The presence of suicidal ideation 1 to 2 will be assessed with "yes" or "no," and if the answer to 2 is "yes," suicidal ideation 3 to 5 will be assessed. If the answer to suicidal ideation 1 or 2 is "yes," the intensity of ideation will also be rated. Intensity of ideation will be rated on a 5-point scale for frequency and duration and a 6-point scale for controllability, deterrents, and reasons for ideation.

The following suicidal behavior will also be assessed with "yes" or "no," and if the answer is "yes," details will be assessed, and the total numbers of each suicide attempt will be recorded.

If there is an actual attempt, actual lethality/physical damage will be rated on a 6-point scale, and if actual lethality/physical damage is 0, potential lethality will be rated on a 3-point scale.

Suicidal ideation:

- 1. Wish to be dead
- 2. Non-specific active suicidal thoughts
- 3. Active suicidal ideation with any methods (not plan) without intent to act
- 4. Active suicidal ideation with some intent to act, without specific plan
- 5. Active suicidal ideation with specific plan and intent

Suicidal behavior:

Actual attempt, non-suicidal self-injurious behavior, interrupted attempt

aborted attempt, preparatory acts or behavior, suicidal behavior, suicide (only for "Since Last Visit")

3.7.5.8 Drug-induced Extrapyramidal Symptoms Scale

The investigator or subinvestigator will use DIEPSS at scheduled time points to assess the following 9 items on a 5-point scale from 0 (none, normal) to 4 (severe). The date and result of assessment will be recorded on the source documents and eCRF.

1. Gait	2. Bradykinesia	3. Sialorrhea	4. Muscle rigidity	5. Tremor
6. Akathisia	7. Dystonia	8. Dyskinesia	9. Global severity	

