2.3 Dosing Rationale

2.3.1 Regimen

The objective of this trial is to evaluate the PK, tolerability, and safety of the brexpiprazole QW formulation administered as single and repeated administration in patients with schizophrenia. The trial design comprises the single administration period (Cohort 1 and, as necessary, Cohort 1') and the repeated administration period (Cohort 2). All cohorts include Period 1 in which subjects will receive the brexpiprazole conventional tablet as a single administration. In each cohort, following a single administration of the conventional tablet, the same subject will undergo a washout period and then receive the QW formulation. The purpose of administering the conventional tablet is set to reduce the effect of interindividual variability on evaluation of the PK profile of the QW formulation.

In the repeated administration period, subjects will receive the brexpiprazole QW formulation once weekly for 5 weeks (a total of 5 administrations). In general, patients on antipsychotic medication could experience AEs soon after therapy is initiated. With this taken into consideration, treatment will begin with a low dose to confirm the safety and tolerability before increasing the dose to the predetermined level. Specifically, a low dose will be used only for the first administration and the predetermined dose will be used for the subsequent 4 administrations in this trial. Four administrations at the predetermined dose is based on the results of a simulation for the QW formulation indicating that 4 once-weekly administrations of the QW formulation are needed for brexpiprazole concentration to reach the steady state.

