3.7 Trial Procedures

Trial assessment time points are summarized in Table 3.7-1 and Table 3.7-2. Acceptable windows for observations, tests, and assessments are shown in Table 3.7-3 to Table 3.7-6.

Table 3.7-1 Schedule of Assessments (Cohort 1 and Cohort 1)								nd Co	ho	ort	1'	[a	s N	lec	es	sai	ry]	; Singl	e Adr	nin	is	tra	atio	on	Pe	erio	od))										
Treatment Period	Screening			Pe	riod	1 (2	mg	Conve	ntior	al T	ablet))					Р	eriod	2 (24	mg (QW	Form	nulatio	n)				Pe	riod	3 (48	mg	QW	Form	ulatio	n)		۹ ⁰	Follow-up
Day	-28 to -1			1			2	3	4	6	8	11	14			1		1	2	3	4	6	8	14			1			2	3	4	6	8	11	14	ly atio	
Hours postdose		Predose	0 2	4	6 8	12	24	48	72	120	168	240	312		Predose	0	3 9	24	36	48	72	120	168	312		Predose	0	3 9	24	36	48	72	120	168	240	312	Ear Termin	Days 28- 30
Informed consent	X																																					
Informed consent to CYP2D6 genotyping	X]																								
Informed consent to blood sampling for DNA storage (optional)	X																																					
Inclusion/exclusion criteria	X																																					
Demographics (including height)	X																																					
Urine drug screening	X														X	1										Xf												
Pregnancy test (women of childbearing potential only)	х	\mathbf{X}^{f}											X		x	,								Х		\mathbf{X}^{f}										x	X	
Blood sampling for CYP2D6 genotyping		X]																								
Blood sampling for DNA storage (optional)		x																																				
Subject enrollment	X	X												م	X										9d	Х												
IMP administration		2	x											erie		X									erie		X											
Blood sampling for plasma drug concentration measurement		Xg	X	x	x	х	Х	X	x	x	Х	x	x	hout p	X		xx	x	x	x			Х		hout p	\mathbf{X}^{g}		xx	x	x	x	x	х	Х	х	X	X	
Clinical laboratory tests ^d	X												X	Was						X			Х		Was						X			Х		X	X	
Physical examination	Х	Xg					Х				Х		X	1	X	;	ΧХ	XX	X	X	X	Х	Х	X	r.	Xg	\square	xх	X	X	X	Х	Х	Х	Х	X	X	X
Vital signs (blood pressure, pulse rate, body temperature)	х	Xg					х				х		x		X	;	Х	x		x	x		х	X		Xg		x	x		x	x		x		x	X	
Weight	Х	Xf											X		X								Х	X		Xf	\square							Х		X	X	
12-lead ECG ^e	Х	X ^{a,f}					Х						X				Х	X			X		Х	X			\square	X	X			Х		Х		X	X	
DIEPSS		Xf									Х		X	1	X						X		Х	Х		Xf	\square					Х		Х		X	X	X
C-SSRS	Х	Xf					Х				Х		X	1	X			X		X	X	Х	Х	Х		Xf	\square		X		X	Х	Х	Х	Х	X	X	
CGI-S		Xf									Х		X	1	X	7							Х	Х		Xf	\square							Х		X	X	
CGI-I											Х		X	1									Х	Х			\square							Х		X	X	

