Hours postdose		Predose	0 2	4 6	8	12	24 4	8 72	120	168	240	312		Dradoca	Administration	€9				Dradoea	Predose Administration	(2)	9					Administration	(5)			Predose	Administration (4) ^h			Predose	Administration (5)	3	9 24	4 36	48	72 12	20 10	68 24	40 31	12 I2	Days 56-60	
Informed consent	X			-		-	+	-							-				-								-		+										-				+		-			1
Informed consent to CYP2D6 genotyping	Х																																															
Informed consent to blood sampling for DNA storage (optional)	х																																															
Inclusion/exclusion criteria	X																																						-									
Demographics (including height)	Х																																															
Urine drug screening	Х													Х	f																																	٦
Pregnancy test (women of childbearing potential only)	x	\mathbf{X}^{f}										х		Х	f																														3	x x		
Blood sampling for CYP2D6 genotyping		X		-									òđ																-										_									1
Blood sampling for DNA storage (optional)		X											ıt peri																																			
Subject enrollment	X	X					-			-			hou	2	(-	-									-																			
IMP administration			X	-									Was		X	:						x						X					X				Х		_									1
Blood sampling for plasma drug concentration measurement		Xg	X	x x	x :	x	x x	x	x	x	x	х		х	g					х	Kg						,	Xg				Xg				Xg		x	x x	x	x	хУ	()	x x	х 3	x x		
Clinical laboratory tests ^d	X											Х						x		>	Xf			Х	:)	Xf				Xf				Xf										x x		
Physical examination	X	Xg				1	x			X		Х		x	g	X	X	X	хΣ	< x	x ^g	2	x D	ΧХ	: x	: x	ι,	x ^g	X	ĸ	Х	Xg		X	х	Xg		X	x x	x	X	х х	()	x y	x J	x x	X	
Vital signs (blood pressure, pulse rate, body temperature)	x	Xg				3	x			x		х		x	g	x	x	x	x	х	Kg	2	x z	х х	x	:	2	X ^g	x	ĸ	х	Xg		x	х	Xg			x	:	x	x	:	x	,	x x		
Weight	X	Xf										Х		x	f					,	xf						,	Xf				Xf				Xf			_	-					7	x x		
12-lead ECG ^e	X	X ^{a,f}				1	x					х				X	X	1	x	, ,	xf	2	x :	ĸ	X	:	,	x ^f	X	ĸ	Х	Xf		x	Х	Xf			X			x		x		x x		1
DIEPSS		Xf								X		х		X	f			1	x	>	Xf				X	:	,	Xf				Xf				Xf								x	3	x x	x	1
C-SSRS	x	Xf		-		1	x			X		Х		X	f		X	X	ΧУ	< y	Xf		3	х х	X	X	()	Xf	X	ĸ	Х	Xf		x	Х	Xf			X	:	X	ΧУ	()	x J	x J	x x		1
CGI-S		Xf		-						X		Х		X	f					>	Xf						,	Xf	-			Xf				Xf			-					x	3	x x		1
CGI-I				-						X		Х								>	xf						,	X ^f				Xf				Xf			-	-			1	x	3	x x		1
Adverse events	<			-	FF	-	+	-	-	-					-				-	-		-	-	-	-	-	-		-	-				-					+	+	F	-	-		+	-	>	-

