Concomitant medications and therapies	<																																						-		\square					->		
Hospitalization period	Outpatient visits				Hos	pitali	zation	1			Outpa vis	atient									Нс	spitaliz	zation							Oı	utpatient visits	Hos	oitalizati	on	Outpatient visits			1	Hospi	italizat	ion			0	utpatic	ent vis	its permitte	d
	permitted										perm	ntted																		pe	ermitted				permitted													

Note 1: This table shows time points for assessments and should be used together with Section 3.7.3 Schedule of Assessments, which summarizes the timing of assessments and activities by trial period/trial day.

Note 2: The doses of the QW formulation may be changed depending on the results of Cohort 1 and Cohort 1' (as necessary) (single administration period) (Section 3.2 Trial Treatments).

^aIf IMP administration takes place within 14 days after the same test was performed during screening, a repeat test is not required.

^bIf the subject refuses an early termination (ET) assessment or if the investigator or subinvestigator finds it impossible to perform an ET assessment in emergencies or for other reasons, only feasible observation/tests will be performed.

^cA washout period of 20 days (+ 8 days max) will be placed between IMP administration in Period 1 and IMP administration in Period 2.

- ^dA thyroid function test will be performed only at 1 time point: screening.
- ^eMust be performed prior to blood sampling for plasma drug concentration measurement and clinical laboratory tests.
- ^fMust be performed within 1 day predose.
- ^gMust be performed within 2 hours predose.
- ^hWith Day 1 defined as the day of the first administration, administration on Days 8, 15, and 22 must take place within ± 24 hours of the clock time when the first administration occurred.
- ⁱWith Day 1 defined as the day of the first administration, administration on Day 29 must take place within ± 5 hours of the clock time when the first administration occurred.

Table 3.7-3AcAssCoNeCo	ceptable Windows for Observations, Tests, and sessments Following a Single Administration of nventional Tablet (Period 1 of Cohort 1 and Cohort 1' [as cessary] [Single Administration Period] and Period 1 of hort 2 [Repeated Administration Period])
Time Point	Acceptable Window for All Observations, Tests, and Assessments (Including Blood Sampling for Plasma Drug Concentration
	Measurement)
Predose	Blood sampling for plasma drug concentration measurement, physical

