blood sampling in Period 3 of the single administration period (Cohort 1 and Cohort 1' [as necessary]) and for the fifth administration in Period 2 of the repeated administration period (Cohort 2) to cover the PK process from absorption to elimination. For each of the first to fourth administrations of the QW formulation, 168 hours postdose, the time point of trough concentration, was set for blood sampling to ascertain if the plasma brexpiprazole concentration has reached the steady state. In addition, a total of 7 time points, namely, predose and 3, 9, 24, 36, 48, and 168 hours postdose, were set for blood sampling in Period 2 of the single administration period (Cohort 1 and Cohort 1' [as necessary] to obtain samples for use in estimation of parameters with a population PK analysis model.

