9.7 Other Safety Data

9.7.1 DIEPSS

For the DIEPSS total score (sum of items 1 to 8) and the score for each item, descriptive statistics of actual measurements and changes from baseline at each time point will be produced.

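### In Cohort 2 every scheduled DIEPSS rating from the third dose on falls at or after trough, so the DIEPSS tables do not sample the steady-state peak; moving one rating would close the gap

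*Protocol*

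**What the plan says.** Protocol 3.7.5.8 states that "The investigator or subinvestigator will use DIEPSS at scheduled time points to assess the following 9 items on a 5-point scale". The timing is in the schedule tables: "Trial assessment time points are summarized in Table 3.7-1 and Table 3.7-2" (Protocol 3.7).

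In Table 3.7-2, Cohort 2 Period 2, DIEPSS is scheduled at:

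- Day 1 predose, Day 4, Day 8 predose and Day 11;
- predose on Days 15, 22 and 29;
- Day 36 (168 h after dose 5), Day 42 (312 h), early termination, and follow-up on Days 56 to 60.

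Nothing is scheduled between 0 and 168 h after doses 3, 4 or 5. In Cohort 1 (Table 3.7-1), DIEPSS is rated 72 h after each QW dose.

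Protocol 3.7.6.1.2 describes "168 hours postdose, the time point of trough concentration". Protocol 2.3.1 reports a simulation in which "4 once-weekly administrations of the QW formulation are needed for brexpiprazole concentration to reach the steady state", which places steady state at dose 5. SAP 9.7.1 says that, for DIEPSS, descriptive "statistics of actual measurements and changes from baseline at each time point will be produced", and SAP 3.4 uses nominal time points.

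**The concern.** Tolerability is part of the trial objective (Protocol 2.4), DIEPSS is a named safety endpoint (3.5.2), and the upper bound of the target PK profile is a peak concentration (2.1). At steady state on the target regimen, the DIEPSS tables will describe trough exposure and later. A flat change from baseline there would say little about extrapyramidal symptoms around the peak, yet could be read as if it did. The schedule gives no reason for having no mid-interval rating after dose 5, although subjects are inpatients on Days 29 to 36 and other assessments are made through that interval.

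**Working it through.** **Reading the table.** The columns of Table 3.7-2 break up in text form, so the DIEPSS marks were aligned with the physical examination, C-SSRS and CGI-S rows. All four rows agree on the positions of Day 29 predose, 168 h and 312 h. The DIEPSS row is empty from 3 h to 120 h after dose 5. The reading should be confirmed on the laid-out table.

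**Inputs from the protocol**

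- Table 1.2-2, QW-A 12 mg: median tmax 30.13 h (range 23.25 to 49.57), mean half-life 71.5 h.
- Table 1.3-1, simulated 48 mg at steady state: Css,max 176 and Css,min 55.1 ng/mL.
- Dosing windows: "administration on Days 8, 15, and 22 must take place within ± 24 hours of the clock time when the first administration occurred"; "administration on Day 29 must take place within ± 5 hours of the clock time when the first administration occurred".
- Rating windows: predose DIEPSS within 1 day before the dose; 168 h ± 4 h.

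**Step 1: trough against peak.** 55.1/176 = 0.313. The simulated peak is about 3.2 times the level at a 168 h rating.

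**Step 2: could the windows bring a rating near the peak?** Earliest time since the previous dose, with every window at its extreme:

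- Days 15 and 22: 168 − 48 − 24 = 96 h
- Day 29: 168 − 24 − 5 − 24 = 115 h
- Day 36: 168 − 4 = 164 h

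All are well past the longest observed tmax, 49.57 h. Assume log-linear decline from Css,max at tmax to Css,min at 168 h, so that k = ln(176/55.1)/(168 − tmax). With tmax = 30.13 h, k = 1.161/137.87 = 0.00842 per h, and the level at 96 h is exp(−0.00842 × 65.87) = 57% of peak. Over tmax 23.25 to 49.57 h it is 56% to 63%. Even the extreme case is far from the peak.

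**Step 3: level at Day 42.** From trough, 144 h later, at half-life 71.5 h: 55.1 × 2^(−144/71.5) = 13.6 ng/mL, about 8% of peak.

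**Step 4: other days (assumed model, not a protocol result).** One compartment with zero-order input over T hours. Per unit dose, the level is (1 − e^(−kt))/(kT) up to T, and (1 − e^(−kT))e^(−k(t−T))/(kT) afterwards. These are summed over 24 mg at 0 h and 48 mg at 168, 336, 504 and 672 h. The half-life is varied over 71.5, 90 and 107 h. The lower end is from Table 1.2-2; the upper end is the rounded 106.83 h in Protocol 1.2.2.1. T is varied over 24, 30 and 36 h (assumed). Results as a percentage of the peak after dose 5:

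| Rating | % of peak |
|---|---|
| Day 11 (72 h after dose 2) | 55 to 63 |
| Day 15 predose | 22 to 33 |
| Day 22 predose | 24 to 40 |
| Day 29 predose | 25 to 42 |
| Day 36 | 25 to 43 |
| Day 42 | 6 to 17 |
| Day 31 (48 h after dose 5, not now scheduled) | 79 to 93 |

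Example: with half-life 71.5 h and T = 24 h, k = 0.00969 and the peak is at 24 h. Day 31 is then exp(−0.00969 × 24) = 79% and Day 36 is exp(−0.00969 × 144) = 25%. In the same model, the Cohort 1 rating 72 h after a single 48 mg dose is at 49% to 57% of the Cohort 2 peak, so Cohort 1 does not fill the gap.

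**Step 5: is the weekly peak above daily dosing?** In Table 1.3-2 the mean steady-state peaks with 4 mg daily are 164.63, 170 and 199 ng/mL, and with 2 mg daily 81.2 ng/mL. The simulated 176 ng/mL lies inside the 4 mg range and above 2 mg.

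**The case against.** The schedule has a reason behind it. Protocol 2.3.1 names adverse events soon after initiation as the risk, and the two mid-interval ratings fall after the starting dose and the first increased dose. That explains Days 4 and 11, and it stands.

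A reader might infer that spontaneous adverse event reports are the only extrapyramidal information near the peak. The documents contradict this. Physical examinations run through the dose-5 interval and cover limbs and nerves, and new clinically relevant findings become adverse events (3.7.5.4). Adverse events are elicited by a standard question (5.2). DIEPSS is required before new or increased antiparkinsonian use (4.3). None of these gives a graded change from baseline for the whole cohort, and the triggered ratings reach only subjects with symptoms and have no nominal time point.

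A reader might also infer that the weekly form is known to peak above daily dosing. Step 5 does not support that.

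The absolute levels are uncertain. Four times the observed 12 mg Cmax is 61.11 × 4 = 244 ng/mL, above the simulated steady-state 176. On that scaling a Cohort 1 rating at 72 h would be at 244 × 2^(−41.87/71.5) = 163 ng/mL, 93% of 176. But the steady-state peak would then be higher too, so this does not show that Cohort 1 covers it. It does mean that the percentages are approximate.

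Finally, the documents give no DIEPSS recall period and no exposure-response relation for extrapyramidal symptoms. DIEPSS enters no progression or dose-increase withdrawal criterion. Cohort 2 is a small, uncontrolled cohort whose subjects may take other antipsychotics. One more rating could not attribute symptoms to the peak. These points limit the weight of the finding without removing the gap.

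**Conclusion.** The point holds as a limit on what one safety endpoint can show. From dose 3 on, no scheduled DIEPSS in Cohort 2 falls near the steady-state peak: ratings are nominally at 168 h or later, against a tmax of about 23 to 50 h and a simulated trough/peak ratio of 31%. The timing conclusion rests on the table reading and the stated windows; the percentages for the other days rest on the assumed one-compartment model. The gap concerns documenting tolerability at the target regimen's peak. It is neither an absence of extrapyramidal monitoring nor an established excess of exposure over daily dosing. The change is inexpensive and worthwhile, but optional.

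**What to change.** In Table 3.7-2, move the predose Day 22 DIEPSS to Day 31 of Period 2 (48 h after dose 5, window ± 2 h). Keep predose Day 29 and Day 36 as the trough ratings. Subjects are inpatients on Day 31, with physical examination, C-SSRS and PK sampling already scheduled, so no visit or rating is added. SAP 9.7.1 needs no new wording, because it already summarises each time point.

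The costs are a schedule amendment, one fewer intermediate trough rating, and a change in when the existing rule against antiparkinsonian drugs in the 12 hours before DIEPSS applies (Day 31 instead of Day 22). If the schedule stays as it is, the report should state that the steady-state DIEPSS results describe trough and later exposure.
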